#### **2.3.4.1 Demographics and baseline characteristics**

Demographic variables include:

- Age (years), age group (derived; < 65 years, 65 to <75 years, and  $\geq$  75 years)
- Sex (Male, Female, Unknown, Undifferentiated)
- Race (White, Black, Asian, Native Hawaiian or Other Pacific Islander, American Indian or Alaska Native)
- Ethnicity (Hispanic or Latino, Not Hispanic or Latino, Not Reported, Unknown)
- Total subjects recruited under each country (Total recruited, Recruited in Canada, Recruited in the US)

Baseline characteristic variables include:

- Height (cm)
- Weight (kg)
- BMI ( $\text{kg}/\text{m}^2$ ) [ $= \text{weight} (\text{kg})/\text{height} (\text{m})^2$  from screening visit 1]
  - BMI categories (< 20, 20 to < 25, 25 to 30,  $\geq$  30  $\text{kg}/\text{m}^2$ )
- Smoking history (Former, Current, Never)
- Heart rate (beats per minute)
- Bundle branch block (or Intraventricular conduction delay [IVCD]) present (No, Yes)
  - Bundle branch block type (Left bundle branch block, Right bundle branch block, Non-specific IVCD)
- NT-proBNP (pg/mL) values based on clinical laboratory samples processed and assessed by the central laboratory
  - NT-proBNP quartiles and IQR
  - Log-transform of NT-proBNP
- BNP (pg/mL) (screening visit 1 only), based on clinical laboratory samples processed and assessed by the local laboratory
  - BNP quartiles and IQR
  - Log-transform of BNP
- NT-proBNP (pg/mL) (screening visit 1 only), based on clinical laboratory samples processed and assessed by the local laboratory

- NT-proBNP quartiles and IQR
- Log-transform of NT-proBNP

### 2.3.4.2 Disease characteristics

Disease characteristic variables include:

- Category of prior cardiovascular (CV) medication:  
(Diuretic class (Loop diuretic, Thiazide diuretic)), Mineralocorticoid receptor antagonist (MRA), ACEi, ARB, Digoxin, Beta blocker, Calcium channel blocker (CCB), Long-acting nitrate, Anticoagulant class (Warfarin, Direct-acting oral anticoagulants (DOACs)), Aspirin, Statin, Non-statin lipid lowering therapy, Antiplatelet (excluding aspirin), Adenosine diphosphate (ADP) antagonist, SGLT2 inhibitors with relevant Anatomical Therapeutic Chemical (ATC) drug class codes.
- ACEi/ARB naïve (never exposed); Previously on ACEi/ARB but not currently taking (previously exposed); Currently taking (up until randomization).
- Primary HF etiology: Ischemic; Non-ischemic
  - Hypertensive (No, Yes)
  - Diabetic (No, Yes)
  - Alcoholic (No, Yes)
  - Viral cardiomyopathy (No, Yes)
  - Infectious cardiomyopathy (No, Yes)
  - Peripartum (No, Yes)
  - Drug induced (No, Yes)
  - Other (No, Yes)
- History of HF prior to qualifying HF event (No, Yes, Unknown)
- Number of hospitalizations with primary diagnosis of HF within past 12 months not including qualifying hospitalization
  - Number of hospitalizations categories (0, 1, 2,  $\geq 3$ , Not Applicable)
- Total number of hospitalizations for any reason within past 12 months
- NYHA classification approximately 1 month prior to admission of the trial (I, II, III, IV, Unknown)
- Most recent left ventricular ejection fraction (LVEF) (%)
- Left ventricular ejection fraction (LVEF) categories prior to randomization:
  - $> 40$  to  $< 45\%$  vs.  $\geq 45\%$ ;
  - $> 40$  to  $< 50\%$  ((HFmrEF (mildly reduced) ),  $\geq 50\%$  ( (HFpEF) preserved )
  - $\geq 50$  to  $\leq 60\%$  vs.  $> 60^*$
  - $> 40$  to  $\leq 60$  vs.  $> 60^*$
  - $\leq$  median vs.  $>$  median)
- Left atrial enlargement defined by at least one of the following:
  - LA width  $\geq 3.8$  cm
  - LA length  $\geq 5.0$  cm

- LA area  $\geq$ 20 Square Centimeter
- LA volume  $\geq$  55 mL 28
- LA volume index  $\geq$  29 Milliliters per Square Meter
- Left ventricular hypertrophy (Septal thickness or posterior wall thickness  $\geq$ 1.1 cm,
- Time from hospital presentation to randomization (days)
- Any prior EF < 40% (LVEF < 40%) (No, Yes, Unknown)
- Presence of structural heart disease (No, Yes, Unknown)

\* LVEF of >60% is defined as normal; LVEF  $\leq$  60% is defined as “below normal”

### **2.3.4.3 Cardiovascular history**

Cardiovascular history will be summarized. The following disease information will be collected:

- Hypertension (No, Yes, Unknown)
- Transient ischemic attack (No, Yes, Unknown)
- Stroke (No, Yes, Unknown)
- Peripheral vascular disease (No, Yes, Unknown)
- Chronic renal insufficiency (CRI) [eGFR  $<$ 60 ml/min/1.73m^2 prior to qualifying hospitalization or WHF event] (No, Yes, Unknown)
- Chronic kidney disease (CKD) stage (CKD Stage 3 [eGFR 30 to 59], CKD Stage 4 [eGFR 15 to 29], CKD Stage 5 [eGFR  $<$  15 or dialysis] and Other
- CKD defined as either CRI=yes or CKD stages (3 or 4 or 5) =yes. (No, Yes, Unknown)
- eGFR categories prior to randomization
  - $<$  60 ml/min/1.73m^2
  - $\geq$  60 ml/min/1.73m^2
- Arrhythmia (No, Yes, Unknown)
  - Arrhythmia type (AF, Atrial flutter, Supraventricular tachycardia, Ventricular tachycardia)
- Pacemaker/Implantable cardioverter defibrillator (ICD) (No, Yes, Unknown)
  - Device type (Pacemaker [conventional], Cardiac resynchronization therapy – no ICD [CRT-P], Cardiac resynchronization therapy – with ICD [CRT-D], ICD only [single/dual], Other, Unknown)
- Moderate to severe valvular heart disease (No, Yes, Unknown)
  - Heart disease type (Mitral regurgitation, Aortic regurgitation, Aortic stenosis, Tricuspid regurgitation)
- Prior valvular heart surgery (No, Yes, Unknown)
  - Valvular surgery type (Mitral, Aortic, Tricuspid, Pulmonic)

#### **2.3.4.4 Non-Cardiovascular Medical History**

Non-cardiovascular medical history and ongoing conditions will be summarized and listed. The summaries will be presented by primary system organ class (SOC), preferred term (PT) and treatment group for both double-blind and open-label subjects. Incidence of SARS-CoV-2 (COVID-19) infection in the subjects' medical history will be included in the non-cardiovascular medical history summaries and listings. Non-cardiovascular medical history and ongoing conditions will be coded using Medical Dictionary for Regulatory Activities (MedDRA) terminology (latest version at the time of data cut-off will be used).

#### **2.3.4.5 Surgeries and Medical Procedures**

Surgeries and medical procedures will be listed, including the reason, start date and end date. Surgeries and medical procedures will be coded using MedDRA terminology (latest version at the time of DBL will be used).

### **2.4 Treatments (study treatment, rescue medication, concomitant therapies, compliance)**

The SAF will be used for all analyses associated with study treatment and medications, unless otherwise specified.

#### **2.4.1 Study treatment / compliance**

The duration of study treatment is defined as:

*Duration (days) = (date of last study treatment – date of first study treatment) + 1*

The first date of study treatment is recorded on the First Dose of Study Treatment eCRF.

Summary statistics will be displayed for the duration of study treatment by treatment group and in-hospital/out-of-hospital randomization category using mean, SD, median, minimum, and maximum. Additionally, the number and percentage of participants will be summarized by treatment group and in-hospital/out-of-hospital randomization for duration category.

The durations will also be categorized into weekly time intervals (< 7 days, 7 to < 14 days, 14 to < 21 days, ..., etc.). The number and percentage of subjects in each category will be presented.

Total subject-days of exposure will also be summarized.

In addition, the number and percentages of each dose level dispensed by visit will be summarized by treatment group. The number and percentage of the maximum dose levels dispensed will also be presented by treatment group. Similarly, the up-titrated doses, down-titrated doses and unchanged doses will be summarized by visit and treatment group. The number and percentage of subjects who were dispensed Dose Level 3 by Week 6 will be summarized by treatment group.

All information on dose administration will be listed.

The duration of exposure by pandemic impact may also be summarized.

## **2.4.2 Prior, concomitant and post therapies**

### **2.4.2.1 Prior and concomitant medications definition**

Prior and concomitant medications will be coded according to the World Health Organization (WHO) Drug Reference List (latest version at the time of data cut-off will be used). Prior and concomitant medications are mutually exclusive, as defined below:

- Prior medications are defined as any medication with an end date prior to the first dose of study treatment
- Concomitant medications are defined as any medications taken on or after the start of study treatment. Prior medications that are 'ongoing' at the time of the first study treatment or whose end date is after first study treatment will be considered a concomitant medication

The number and percentage of subjects with concomitant medications that started after study treatment will be summarized by ATC class, PT and study phase (refer to [Section 2.1.1](#) for study phase definitions). All medications will be listed. Concomitant medications and significant non-drug therapies, prior to and after the randomization, will be summarized by therapeutic class, PT, treatment group, and in-hospital/out-of-hospital randomization category. The SAF population will be used for the above analyses.

### **2.4.2.2 Medications of interest**

The following medication classes of interest will be summarized by treatment group and in-hospital/out-of-hospital randomization status at Baseline:

- Previous use of medication, n(%)
- Any Diuretic agent
  - a) Diuretics prior to index (qualifying event)
  - b) Loop diuretics
    - ACEi or ARB
    - MRA
    - BB
    - SGLT2i

Medication names will be coded using the WHO Drug Reference List (latest version at the time of Database Lock will be used).

### **2.4.2.3 COVID-19 vaccination status**

COVID-19 vaccination status will be summarized by treatment group and by study phase. The descriptive summary will present the number and percentage of subjects who are fully vaccinated, partially vaccinated (received 1 out of 2 doses of vaccine, where applicable). Booster doses will not be included as an indication of full vaccination status, however will be recorded and provided.

Total number of COVID-19 vaccine doses (No vaccine, 1, 2, 3, 4 and 5 (if applicable)) will also be reported along with a complete. Listing for COVID-19 vaccination status.

The SAF population will be used for the above analysis.

#### **2.4.3 Unscheduled visit mapping**

When visit mapping are used, all visits will be re-aligned, i.e., they will be mapped into one of the visit windows. E.g., if the Week 4 visit of a subject is delayed and occurs on Day 46 instead of on Day 29, say, it will be re-aligned to visit window Week 8. In the case of major deviations from the visit schedule, or due to unscheduled visits, several assessments of a subject may fall in a particular visit window (either scheduled or unscheduled). Statistical approaches to handle multiple assessments in a given visit window are specified below in Section 2.4.4.

An unscheduled visit will be mapped according to the following visit windows:

For subjects recruited under Original protocol (00) to Amendment 01-03:

Visit Name	Visit Number	Target Day (Study Days)	Visit Window (Study Days)
Week 1	Visit 3	7	2 to 10
Week 2	Visit 4	14	11 to 21
Week 4	Visit 5	28	22 to 35
Week 6	Visit 6	42	36 to 49
Week 8	Visit 7	56	50 to 63
Week 10	Visit 8	70	64 to 77
Week 12	Visit 9	84	78 to 98
Week 16	Visit 10	112	99 to 140
Week 24	Visit 11	168	141 to 196
Week 32	Visit 12	224	197 to 252
Week 40	Visit 13	280	253 to 308
Week 48	Visit 14	336	309 to 364
Week 56	Visit 15	392	365 to 434
Week 68	Visit 16	476	435 to 532
Week 84	Visit 17	588	>532;

Visit Schedule to be followed for subjects recruited under protocol Amendment 04:

Visit Name	Visit Number	Target Day (Study Days)	Visit Window (Study Days)
Week 1	Visit 3	7	2 to 17
Week 4	Visit 5	28	18 to 42
Week 8	Visit 7	56	43 to 112
Week 24	Visit 11	168	113 to 224
Week 40	Visit 13	280	225 to 336
Week 56	Visit 15	392	337 to 434
Week 68	Visit 16	476	435 to 532
Week 84	Visit 17	588	>532

#### **2.4.4    Multiple assessments within visit windows**

When there are *multiple assessments* in a particular visit window, the following rules are applied to select one value “representing” the subject in summary statistics in a visit window.

In cases where there are multiple assessments in the Screening period, the value closest to the baseline will be considered for the analysis.

For baseline assessment definition see [Section 2.1.1](#). For post-baseline visit windows with multiple assessments, the following applies (unless otherwise specified):

1. for *quantitative variables*, the *closest* to the actual visit is chosen (if two assessments have the same distance, then the earlier one will be chosen);
2. for *qualitative variables*, the *worst* record is selected. It is noted that in the analyses performed, worst case is always well defined.

### **2.5    Analysis of the primary objective**

#### **2.5.1    Primary endpoint**

The primary endpoint is the comparison of the time-averaged proportional change from Baseline in NT-proBNP between sacubitril/valsartan and valsartan to Week 4 and 8.

Primary analysis timepoint will be the change from Baseline to averages of Week 4 and 8.

The analysis of the primary endpoint will be based on the FAS.

#### **2.5.2    Statistical hypothesis, model, and method of analysis**

The primary analysis to address the primary objective will be based on the following estimand:

##### **Estimand 1**

Population: Defined through the appropriate inclusion/exclusion criteria to reflect the targeted study population currently hospitalized for or within 30 days of a WHF event (HFpEF decompensation). A WHF event (HFpEF decompensation) is defined as a hospitalization, emergency department (ED) visit or out-of-hospital urgent HF visit, all requiring IV diuretics.

Endpoint: Time-averaged proportional change between Baseline and weeks 4 and 8 in NT-proBNP

Treatment: The randomized treatment sacubitril/valsartan or valsartan

Intercurrent event: Using a treatment policy strategy to handle the intercurrent event of treatment discontinuation.

Summary measure: Difference between treatment in ratios of geometric means

The primary null hypothesis to be tested is the ratio of the geometric means of NT-proBNP (average of Weeks 4 and 8 divided by Baseline) for the sacubitril/valsartan and valsartan treatment groups are equal ( $H_{10}$ ) versus the alternative hypothesis that the ratio of the geometric means of NT-proBNP are not equal ( $H_{1a}$ ).

For NT-proBNP, the time-averaged proportional change from Baseline in a natural logarithmic scale will be analyzed using an ANCOVA model using data from Weeks 4 and 8 with treatment,

in-hospital/out-of-hospital randomization status, gender, and Baseline LVEF ( $\leq$  Median,  $>$  Median) as fixed effect factors, age and the logarithmic Baseline NT-proBNP as covariates.

The values from Weeks 4 and 8 will be averaged and the change from Baseline in log transformed NT-proBNP will be calculated as follows:

$$\ln(\text{average post dose value}) - \ln(\text{baseline value})$$

The estimated treatment effect in terms of ratios of geometric means, based on the least-squares (LS) means from the model, and the corresponding two-sided 95% confidence intervals (CIs) will be presented.

The geometric means (presented as a ratio to Baseline) will be calculated by exponentially back transforming the LS means based on the ANCOVA model as follows:

$$\exp(\text{LS mean})$$

The FAS will be used for the primary endpoint analysis.

### **2.5.3 Handling of missing values/censoring/discontinuations**

The analysis will be performed based on all available data in the FAS. Missing values caused due to unevaluable samples or early discontinuations will not be imputed.

Also, NT-proBNP from unscheduled visits will not be used for the analysis.

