6.4 Dose modification

6.4.1 Dose modifications

For patients who do not tolerate the protocol-specified dosing schedule, dose interruptions and/or reductions are either recommended or mandated in order to allow patients to continue the study treatment.

Deviations to mandatory dose interruptions and/or reductions are not allowed. Permanent treatment discontinuation is mandatory for specific events listed in [Section 9.1.1](#).

These dose changes must be recorded on the appropriate case report form (CRF).

Every attempt should be made to maintain patients on the target study drug dose level for as long as possible throughout the study. If, however, in the opinion of the investigator, a patient is unable to tolerate the protocol-specified target dose, the investigator should consider whether dose adjustments of concomitant medications may rectify the situation before reducing the dose of study treatment. If adjustment of the concomitant medications is not possible or does not alleviate the side effects of concern, the investigator may down-titrate the dose of the study drug to the previous dose level. If needed, the study drug may be stopped completely, if this occurs, the patient should return to the clinic as soon as possible, after discontinuation of study drug, for an end of study visit. Patients may restart their current dose of study drug following an interruption of treatment, based on investigator judgment.

Study drug dose level adjustments should be mainly based on overall safety and tolerability with special focus on:

- Hyperkalemia
- Symptomatic hypotension
- Clinically significant decrease in eGFR/increase in serum creatinine (defined as a serum creatinine of $\geq 0.5\text{mg/dl}$ with at least a 25% decrease in eGFR)
- Angioedema

These changes must be recorded on the appropriate CRF. Every attempt should be made to titrate to and maintain patients on target study drug Dose Level 3 for as long as possible throughout the study. If, however, in the opinion of the investigator, a patient is unable to tolerate the protocol-specified target dose, the investigator will manage the patient's treatment according to the below guidelines:

Steps:

1. Adjust Concomitant Medications

- Dose adjustments/elimination of concomitant medications may remedy the situation before reducing the dose of study treatment. If adjustment of the concomitant medications is not possible or does not alleviate the side effects of concern, THEN;

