2. Adjust Study Treatment Dose Level

- Down-titrade study treatment to the previous dose level. The patient may continue receiving the lower dose level for a recommended period of 1 to a maximum of 4 weeks.
- A re-challenge to titrate back up to the target dose level should be attempted at 2 weeks, or when patient is deemed stable. THEN:

3. Further Adjust Study Treatment Dose Level

- If tolerability issues are not alleviated despite down-titration by one dose level, the investigator may down-titrade further to the next lower study treatment dose level. The patient may continue receiving the lower dose level for a recommended period of 1 to a maximum of 4 weeks. See Step 5.
- Again, once stable, the patient should be re-challenged with up-titration to the next higher dose level in an attempt to gradually bring the patient back to the target study treatment dose level (Dose Level 3).
- The investigator may choose the next dose level for down- or up-titration according to his or her clinical judgment.

4. Stopping Study Treatment

- If needed, the study treatment may be stopped completely, however, every effort must be made to complete an end of study visit and obtain follow up health status information and NT-proBNP for any patient that withdraws from the study.

5. Study drug restart after temporary treatment interruption

- Once the investigator considers the patient's condition appropriate for receiving the study drug, the investigator should re-start the patient on study treatment at the most appropriate and allowable dose level per his/her medical judgment.
- If tolerated, the patient should be titrated up to the next dose level every 1 to 4 weeks, as per the investigator's judgment.
- In some instances, Dose Level 1 or 2 could be maintained if the investigator considers that the patient's condition would not allow any further up-titration to the target dose of study medication (Dose Level 3). In this case, it would be acceptable to maintain the patient at Dose Level 1 or 2, whichever is the higher and tolerated dose level by the patient, but reasons for not getting to Dose Level 3 need to be captured in the eCRF.
- Should the patient not tolerate the re-start study drug dose level, he/she may be down-titrated again (if appropriate) or discontinued from study treatment.

Patients re-started on the study drug will retain their original randomization and study identification numbers.

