Patients should be seen for all visits/assessments as outlined in the assessment schedule ([Table 8-1](#)) or as close to the designated day/time as possible. Missed or rescheduled visits should not lead to automatic discontinuation. Patients who prematurely discontinue the study for any reason should be scheduled for a visit as soon as possible, at which time all of the assessments listed for the final visit will be performed. At this final visit, all dispensed investigational product should be reconciled, and the adverse event and concomitant medications recorded on the CRF.

If the COVID-19 pandemic limits or prevents on-site study visits, alternative methods of providing continuing care may be implemented. Virtual visits [e.g. phone calls, video visits (preferred)] or visits by site staff/home nursing service to the participant's home

depending on local regulations and capabilities, can replace on-site study visits, for the duration of the pandemic until it is safe for the participant to visit the site again.

Table 8-1 Assessment Schedule

Period	Screening	Double-Blind Treatment (84 week)									
Visit Name	Screening	Randomizati on/Baseline									Study Completion/ End of Study
Visit Number	Visit 1	Visit 2	Visit 3	Visit 5	Visit 7	Visit 11	Visit 13	Visit 15	Visit 16	Visit 17	
Week (Day)	[Day -30 to -1.5 (36hours)]	0 (Day 1)	1 (Day 7)	4 (Day 28)	8 (Day 56)	24 (Day 168)	40 (Day 280)	56 (Day 392)	68 (Day 476)	84 (Day 588)	

X = assessment to be recorded in the clinical database or received electronically from a vendor
S = assessment to be recorded in the source documentation and in the database
H = assessment to be recorded in the source documentation and in the database

² All female patients of childbearing potential will have a serum pregnancy test (hCG) performed at Visit 1 (local lab). A urine pregnancy test will be conducted in the local laboratory for remaining visits

⁴ CV medications will be recorded at time of hospital discharge.

⁵ BNP or NT-proBNP will be assessed at Visit 1 via local laboratory. Only NT-proBNP will be assessed via central laboratory for Visits 2, 3, 5 and 7.

⁶ Health status phone call 4 weeks after study completion.

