9.1 Discontinuation

9.1.1 Discontinuation of study treatment

Discontinuation of study treatment for a patient occurs when study treatment is stopped earlier than the protocol planned duration, and can be initiated by either the patient or the investigator.

The investigator must discontinue study treatment for a given patient if he/she believes that continuation would negatively impact the patient's well-being.

Study treatment must be discontinued under the following circumstances:

- Patient/guardian decision
- Pregnancy
- Use of prohibited treatment as per recommendations in the prohibited treatment section
- Any situation in which study participation might result in a safety risk to the patient
- Following emergency unblinding
- Any severe suspected drug related AE at the investigator's discretion

- Suspected occurrence of angioedema. A patient with any signs or symptoms of clinically significant angioedema should be thoroughly evaluated by the investigator to determine if it constitutes a reason for discontinuation of study medication.
- Depending on the serum potassium, blood pressure, or eGFR, patient may need to have their study drug dose or the dose of another concomitant medication reduced or discontinued; or, if appropriate, have potentially contributing agents adjusted. Refer to appendices for treatment guidelines for hyperkalemia, hypotension or renal dysfunction, respectively.

If discontinuation of study treatment occurs, the investigator should make a reasonable effort to understand the primary reason for the patient's premature discontinuation of study treatment and record this information.

Patients who discontinue study treatment or who decide they do not wish to participate in the study further should NOT be considered withdrawn from the study UNLESS they withdraw their consent (see withdraw of informed consent section.). **Where possible, they should return for the assessments indicated** in the assessment schedule. If they fail to return for these assessments for unknown reasons, every effort (e.g. telephone, e-mail, letter) should be made to contact the patient/pre-designated contact as specified in the lost to follow-up section. This contact should preferably be done according to the study visit schedule.

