## **2.11 Biomarkers**

NT-proBNP will be collected and descriptively summarized by visit, treatment group. NT-proBNP will be measured in all subjects using the central laboratory at Visits 2 (randomization), 3, 5, and 7 (Weeks 0, 1, 4, and 8 respectively). Values and the change from Baseline for each parameter will be summarized by visit and treatment group. Analyses will be based on the FAS.

NT-proBNP values will be based on clinical laboratory samples processed and assessed by the central laboratory.

[figure not shown]

P  
D

Additional analysis of biomarkers is discussed in Protocol [Sections 2.5, 2.7, and 2.13](#).

Biomarker samples from subjects who withdrew consent will not be analyzed by the central laboratory.

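### Does the SAP leave it open whether an early end-of-study NT-proBNP sample enters the primary analysis?

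*SAP*

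**What the plan says.** **Collection.** Protocol 6.4.1 (step 4) tells sites to make every effort to complete an end-of-study visit and "obtain follow up health status information and NT-proBNP for any patient that withdraws from the study". Its general text adds that if study drug is stopped completely, "the patient should return to the clinic as soon as possible, after discontinuation of study drug, for an end of study visit". Protocol 9.1.1 says that patients who stop treatment "should NOT be considered withdrawn from the study UNLESS they withdraw their consent", and asks them to return for the scheduled assessments where possible. Footnote 5 to protocol Table 8-1 sets the schedule: "Only NT-proBNP will be assessed via central laboratory for Visits 2, 3, 5 and 7".

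**Analysis.** SAP 2.5.3, the missing-data section for the primary endpoint, uses all available data in the FAS without imputation and adds that "NT-proBNP from unscheduled visits will not be used for the analysis". Protocol 12.4.2 drops a patient who lacks baseline, or who lacks both Week 4 and Week 8. SAP 2.4.3 says "When visit mapping are used, all visits will be re-aligned, i.e., they will be mapped into one of the visit windows" and illustrates this with a Week 4 visit that is "delayed and occurs on Day 46 instead of on Day 29, say, it will be re-aligned to visit window Week 8". SAP 2.11 says "Biomarker samples from subjects who withdrew consent will not be analyzed by the central laboratory". Protocol 9.1.2 permits US samples not yet analysed at withdrawal to be used, within the terms of the protocol and the consent form. SAP 2.5.2 handles treatment discontinuation by a treatment policy strategy.

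**The concern.** A patient who leaves on Day 30 may give a sample that falls in the Week 4 window of both SAP 2.4.3 tables. That sample could be mapped to Week 4, excluded as unscheduled, or never assayed. No sentence says whether an early end-of-study visit counts as unscheduled. If mapping applied, the label could also depend on protocol version: Day 40 is Week 6 for versions 00 to 03 but Week 4 under Amendment 04.

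Patients who stop drug or leave before Week 8 are not a random subset, and the rule for their last sample could decide whether some of them are in the primary analysis at all. On the likeliest reading, a value that sites are pressed to collect is used neither there nor in sensitivity analysis 1, whose imputation model (SAP 2.5.4) holds only baseline, Week 4 and Week 8. With a treatment policy estimand, that looks like discarding relevant data.

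**Working it through.** **1. Which rule governs?**

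- SAP 2.5.3 is specific to the primary endpoint. SAP 2.4.3 is general, applies only when mapping is used, and is not invoked anywhere in section 2.5. Its companion, 2.4.4, picks a value for summary statistics in a window.
- SAP 2.1.1 (Baseline) and 2.11 tie central NT-proBNP to Visits 2, 3, 5 and 7. A sample from any other visit is off schedule, so 2.5.3 excludes it.
- SAP 2.11 concerns withdrawn consent only. Protocol 9.1.2 says such samples may be used, not that they must be. The SAP declines a permission, which is not a contradiction.
- Treatment policy concerns stopping treatment. SAP 2.1.1 (End of Study) allows a patient to stop treatment and continue in the study, as protocol 9.1.1 does; such a patient can still have Visit 5 and Visit 7 samples. Leaving the study is a missing-data matter: protocol 9.1.2 treats later data as missing after consent is withdrawn, and SAP 2.5.4 imputes missing values.

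**2. The plan's own power figure.** Inputs from protocol 12.8 and SAP section 3: N = 450, 1:1 allocation, ratio 0.77, SD 0.85 on the log scale, two-sided alpha 0.05, 15% missing.

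- Missing: 450 × 0.15 = 67.5. Evaluable: 382.5, or 191.25 per arm.
- Difference: ln(0.77) = −0.2614. SE = 0.85 × √(2/191.25) = 0.0869.
- Two-sample t power: 85.1%. The stated 85% reproduces.

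**3. How much could the sample matter?** The number of early samples is not given. Assume a share u of the 67.5 has a usable one, so that added patients = 67.5u. Three further assumptions about those patients:

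- A: they show the planned effect.
- B: they show no arm difference, so ratio = exp(−0.2614 × 382.5/(382.5 + added)).
- C: they split 2:1 between arms (a1, a2) and their log change is 0.5 worse, so shift = 0.5 × [a1/(191.25 + a1) − a2/(191.25 + a2)].

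| u | Added | A: power | B: ratio, power | C: shift (in SE of 0.0869) | C: ratio range |
|---|---|---|---|---|---|
| 10% | 6.75 | 85.7% | 0.773, 84.5% | 0.0057 (0.07) | 0.766–0.774 |
| 25% | 16.9 | 86.5% | 0.779, 83.5% | 0.0135 (0.16) | 0.760–0.780 |
| 50% | 33.75 | 87.9% | 0.786, 82.0% | 0.0249 (0.29) | 0.751–0.789 |

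**4. Is 50% attainable?** A version-independent rule could use only days that both 2.4.3 tables assign to Week 4 or Week 8: Days 22–35 and 50–63, which is 28 of the 62 days from 2 to 63. If early samples were spread evenly over those days (an assumption), at most 28/62 = 45% would qualify, or 67.5 × 0.45 = 30 patients. The 50% row lies above that ceiling. Days 22–35 alone give 14/62 = 23%, and a patient first sampled on Days 50–63 with no Visit 5 sample should be uncommon. The 67.5 also includes patients without a baseline value (SAP section 3), whom no such rule can bring in. The 10% and 25% rows are the relevant ones.

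**5. The Day 46 example.** Day 46 is Week 8 in the Amendment 04 table (43 to 112) but Week 6 in the table for versions 00 to 03 (36 to 49). The example is right for one table only.

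**The case for a change.** The best case for acting is that the gap is in the text and cheap to close. No sentence classes an early end-of-study visit as scheduled or unscheduled, and none says that the 2.4.3 windows stay out of the primary endpoint. The patients are plausibly informative, and a rule limited to Days 22–35 and 50–63 would treat all protocol versions alike. Protocol 6.4.1 and 9.1.1 also disagree on what happens after drug is stopped, which affects whether Visit 5 and Visit 7 samples exist.

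The wording points stand, including the disagreement between 6.4.1 and 9.1.1. What does not stand is that they leave the primary analysis without a rule. Nor would the proposed use of the early sample be a clear gain:

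- Entering it as Week 4 or Week 8 reverses the exclusion in 2.5.3 and lets a value taken around the time of stopping or leaving stand in for one at a fixed time. That recovers some patients at the price of a less well-defined endpoint, which is a trade-off and not a correction.
- Adding it to the imputation model promises little. It would be observed mainly in patients who lack the later values, so the data hold little information on how it relates to them.

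**Conclusion.** No change to the analysis follows. SAP 2.5.3, read with the visit schedule, already gives the working rule: Visit 5 and Visit 7 samples by nominal visit, with off-schedule samples left out. A sentence confirming this would record what analysts would do anyway. The Day 46 example is a clerical slip. Protocol 6.4.1 and 9.1.1 must be reconciled by the sponsor as a matter of protocol wording; this review takes no view on which should prevail, and the primary model is the same either way.

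The likely size is small: 7 to 17 patients if 10% to 25% of the missing had a usable sample, an expected ratio between 0.760 and 0.780, and a shift of 0.07 to 0.16 standard errors in the 2:1 scenario. Those shares, the 2:1 split and the 0.5 log worsening are assumptions; the documents support none of them and do not give the number of samples. N = 450 and the stated 85% power are unaffected.
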